5.2. Laboratory tests

Not applicable.

5.3. Other investigations

Not applicable.

6. Assessment of efficacy

- Primary efficacy parameters**
 - Eruption of the canine
 - Integrity of the roots of adjacent teeth

Secondary efficacy parameters

- Improvement of canine angulation (root and crown tip)
- In case of expansion or extraction of the deciduous canines:
 - Improvement of transversal and sagittal occlusion

7. Assessment of Safety

7.1. Specification, timing and recording of safety parameters

The following measures will be used to determine subject safety during the study:

- Physical/oral examination
- Radiographic examination
- Frequent follow up
- Adverse event reporting

7.2. Procedures for recording and reporting adverse events (AE)

Every visit is officially reported in the patient's file in order to identify possible problems and keep a track of them. In case of impacted canines, the major adverse event that could possibly occur is root resorption of the adjacent teeth, which is most of the time unpredictable and even inevitable. In case of such inevitable events, everything will be done to limit the possible damage, including prioritizing surgical exposure of the canine in an effort to reduce the damage, or even extraction of the lateral incisor/s in case of advanced root resorption. However, there is no evidence on existing predictors of this situation. In other words, resorption of the lateral incisors remains unpredictable.

7.3. Treatment stopping rules

Treatment or follow up will immediately stop when compliance of the patient becomes a problem or when for one or other reason, the patient or his/her parents/guardians want to discontinue follow up/treatment:

- The patient does not comply with treatment (does not follow the given instructions, misses the appointments).
- The patient's poor levels of oral hygiene compromise the health of the teeth and/or surrounding soft tissues.
- The patient wishes to stop treatment.

8. Statistics

Measures taken to minimize bias:

- Allocation concealment: randomization of the treatment options by a randomization list.
- Blinding measures: measurements of canine inclination on OPG will be taken by two operators, blinded to each other's measurements as well as to the name of the patient, treatment followed or occlusion details.
- Previous power calculation

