Patients in **Subgroup nCLA**, constituting patients with no cross bite present but lacking space for adequate tooth alignment in the dental arch, will be randomly attributed to one of our three usual treatment options, being interceptive maxillary expansion (IME), extraction of the deciduous canines (EXIII), or no treatment (CO). The latter will constitute the control group within Group nCLA, indicative for maxillary permanent canine eruption in case of lack of space in the dental arch. After this interceptive treatment, all the patients will be enrolled in a standard follow up protocol. In case of absence of deciduous maxillary canines, randomization will not be possible. These patients will still be treated with expansion because of the lack of space and will also be enrolled in subsequent follow-up.

Patients in **Subgroup nCLB** will also be randomly attributed to one of these three usual treatment protocols, being interceptive maxillary expansion (IME), extraction of the deciduous canines (EXIII), or no treatment (CO). The latter will constitute the control group within Subgroup nCLB. After this interceptive treatment, all the patients will be enrolled in a standard follow up protocol. In case of absence of deciduous maxillary canines, randomization will not be possible. These patients will still be treated with expansion because of the lack of space and will also be enrolled in subsequent follow-up.

Subgroup nCLC, constituting the patients with no cross bite present but lacking space for adequate tooth alignment in the dental arch and with very badly positioned and angulated permanent maxillary canine(s), will receive interceptive maxillary expansion (IME) using the standard expansion techniques described above and commonly applied in the university hospital. Patients in Subgroup nCLC, after receiving interceptive expansion treatment, will be further subjected to extraction of the deciduous canine at 6month follow-up, whenever still present in the dental arch, as well as, depending on the severity of canine angulation and position, of the first deciduous molar. Decision for extraction of one or both of these deciduous teeth will be the responsibility of the treating dentist who will have to evaluate the clinical circumstances presenting in this patient with

very badly positioned permanent maxillary canines. Sequence of eruption other than 3-4-5 will also constitute a criterion for extraction of these deciduous teeth.

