After this interceptive treatment, which will last for a maximum of 6 months, all patients will be enrolled in a standard follow up protocol, requiring a minimum of 3 recall visits at 6, 12 and 18 months.

[figure not shown]
2. Non cross bite group with normal adequate space.

Accordingly, Group nCN will constitute all other eligible patients, consecutively seen at the first consultation of the Department of Orthodontics, with one/two impacted permanent maxillary canines without cross bite and showing normal adequate space in the dental arch for tooth alignment. Also these subjects will be categorized into the three subgroups A, B and C. They will receive no interceptive treatment (CO) at all except for subgroup nCNC, constituting of patients with normal alignment and adequate amount of space present but presenting with very badly positioned and angulated permanent maxillary canines. They will be further subjected to extraction of the deciduous canine (EX-III), whenever still present in the dental arch, as well as, depending on the severity of canine angulation and position, of the first deciduous molar (EX-IV). Decision for extraction of one or both of these deciduous teeth will be the responsibility of the treating dentist who will have to evaluate the clinical circumstances presenting in this patient with very badly positioned permanent maxillary canines. Sequence of eruption in the maxilla other than 3-4-5 (canine, first and second premolar) will also constitute a criterion for extraction of these deciduous teeth

After this intervention, all patients in this Subgroup nCN will be enrolled in a standard follow up protocol, requiring minimum one recall visit at 12 months for follow up of normal eruption, eventually a second one after 24 months, provided the maxillary permanent canine is not erupted yet, its root is still not completely formed and no other orthodontic treatment needs are present.

All subjects included in this trial will eventually be subjected to the described follow up procedures, which are described in more detail in Chapter 5. The follow up procedure is designed in order to detect positional changes of the permanent canine position, either spontaneous changes in the control group or changes associated with the interceptive measures taken. Follow up is a necessary and standard procedure for pointing out impacted canines and their true indication for surgical exposure of this tooth.

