3.5. Study diagram

3.6. Trial Flowchart

	Screen visit	Record collection	Third visit	Follow up 6 months	Follow up 12 months	Follow up 18 months	Follow up End result
Informed consent		X					
Physical/Oral examination	X			X	X	X	X
Clinical photograph (if needed)		X		X	X	X	X
Panoramic radiograph (if needed)	X						X
Long cone apical radiograph (if needed)	X			X	X	X	
CBCT scan (if needed)					X		
Identification as potential inclusion in the study	X						
Inclusion in one of the groups and randomized treatment assignment		X					
Start of the assigned treatment (expansion, extraction deciduous canine/molar or no treatment)			X	X	X	X	
Surgical exposure of the maxillary permanent canine					X	X	

4. Selection and withdrawal of subjects

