8.1. Sample size

Randomisation into expansion, extraction and control will be applied for patients without cross-bite having lack of space and – based on canine position and angulation - belonging to strata nCLB and nCLA. Within each of both strata, a randomisation will be performed using permuted blocks of varying size, yielding an equal number of patients in each of the three groups.

Success of the approach is defined as eruption without necessity of surgical intervention and integrity of the roots of the adjacent teeth. The primary endpoint is defined as the percentage success after 18 months. The trial is powered to show a difference between any of the pairs of groups. To have at least 80% power to show a higher success rate in one group compared to the other group, there are 78 subjects needed in each group assuming a success rate of 50% in the first group and 75% in the second group. The calculation is based on a two-sided χ^2 -test with alpha set at $0.05/3=0.0167$ to control the family-wise error rate at 5% (3 pairwise comparisons). However, to increase the amount of information for the development of a prediction model for success at 18 months (cfr. second aim of the study) it has been decided to increase the number of patients to 100 per group (300 patients in total).

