8.2. Analysis

The analysis of the primary endpoint will be based on a stratified χ^2 -test using a Bonferroni-Holm correction to correct for multiple testing (the strata are nCLB and nCLA). The same approach will be used for the comparison at the earlier timepoints (6 and 12 months). No interim analyses are planned, neither for efficacy, nor for futility. The analysis will be performed on an intent-to-treat basis.

A multivariable logistic regression model will be used to predict maxillary permanent canine impaction (=lack of success) on all included subjects. A backward selection procedure will be applied with 0.157 as critical level for the p-value. This critical value corresponds to the use of the Aikake Information Criterion (AIC) for model selection. With AIC we require that the increase in model χ^2 has to be larger than two times the degrees of freedom. This strategy provides a trade-off between erroneous inclusion and exclusion of covariates in a prediction model (Sauerbrei W. The use of resampling methods to simplify regression models in medical statistics. *Applied Statistics* 1999;48 (3):313–329.). The considered predictors are: strata formed by presence of cross-bite and parameters related to canine position and angulation, non-eruption, interceptive strategy, patient's age, stage of canine root formation, premature loss of deciduous teeth, familial history, space deficiency (arch length discrepancy).

As a sensitivity analysis, the prediction model will also be applied separately on the patients from the randomized and non-randomized part of the study.

9. Quality assurance

During this randomized clinical trial only standard operating procedures will be employed, such as i.e. removable expansion device, fixed expansion device, headgear, etc.. They are all validated, thoroughly described and widely used techniques. It will be up to the treating professional to decide for a given case which procedure to follow, in line with existing traditions in the specific collaborating centres. However, the main purpose should be attained which is expansion or in other words gaining extra space for tooth alignment. Depending on the interceptive treatment to be accomplished, decision will be taken to employ one specific treatment protocol to reach the goal set forward.

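### Section 7.3 lets follow-up stop, as well as treatment, for poor compliance; no text keeps 18-month outcome collection going or says how a missing outcome enters the intent-to-treat analysis

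*Combined protocol and SAP*

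**What the plan says.** Section 7.3 (Treatment stopping rules) opens: "Treatment or follow up will immediately stop when compliance of the patient becomes a problem", or when the patient or family wants to discontinue. Its list covers not following instructions, missing appointments, oral hygiene poor enough to harm teeth or soft tissues, and the patient's wish to stop treatment.

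Section 3.4 (Trial Design) says of the randomised strata nCLA and nCLB: "After this interceptive treatment, all the patients will be enrolled in a standard follow up protocol". It adds more generally: "All subjects included in this trial will eventually be subjected to the described follow up procedures". Neither sentence mentions patients stopped under 7.3.

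Section 8.1 sets the endpoint: "The primary endpoint is defined as the percentage success after 18 months". It defines the outcome thus: "Success of the approach is defined as eruption without necessity of surgical intervention and integrity of the roots of the adjacent teeth". Section 8.2 says: "The analysis will be performed on an intent-to-treat basis". It gives no rule for a missing outcome. The only sensitivity analysis in 8.2 concerns the prediction model.

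The flowchart in 3.6 puts "Inclusion in one of the groups and randomized treatment assignment" at the record-collection visit. Under 5.1, the assigned option starts at the third visit, if the patient decides to go ahead. A patient can therefore be randomised and never start.

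**The concern.** Assigning patients to their randomised arm does not supply an 18-month outcome for someone whose follow-up was ended. If 7.3 is followed literally, patients who would have come to the recalls can be lost because of their behaviour after randomisation. The arms differ in how much compliance they demand. Section 5.1 gives expansion an average of 4 and a maximum of 6 consultations over up to 6 months, possibly followed by 2 months of night wear. It describes nothing comparable for the untreated control. That is a plausible mechanism for unequal loss, though not evidence of it.

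If loss differs by arm and is related to outcome, the primary comparison is biased. Leaving lost patients out favours the arm with more loss if they do worse than that arm's average, and penalises it if they do better. Counting them as failures penalises that arm whenever some of them would have succeeded. As written, the choice between these can be made after the data are seen.

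**Working it through.** **The plan's own figure.** Inputs from 8.1: success 50% and 75%, two-sided alpha 0.05/3 = 0.0167, power 80%. The pooled chi-square formula is

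n = [z(1−α/2)·√(2p̄(1−p̄)) + z(0.80)·√(p1(1−p1) + p2(1−p2))]² / (p2−p1)²,

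with p̄ = 0.625. This gives [2.394 × 0.6847 + 0.8416 × 0.6614]² / 0.0625 = 77.1, so 78 per group, as stated. Power is 80.5% at 78 and 90.3% at 100 per group. The sample-size arithmetic is sound.

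**Bias when there is no true difference.** Assumptions not in the documents: true success 50% in both arms, 100 per arm in two equal strata, a share d lost, and success q among the lost. Observed success is

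- completers only: (0.50 − d·q)/(1 − d);
- lost counted as failures: 0.50 − d·q.

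Suppose 10% are lost in each arm whatever 7.3 says, and the rule adds 10 points of loss in one arm (20% versus 10%). The differences (higher-loss arm minus the other) are:

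| q | Completers | Lost as failures |
|---|---|---|
| 0.3 | 0.550 − 0.522 = +2.8 points | 0.44 − 0.47 = −3 points |
| 0.5 | 0.500 − 0.500 = 0 | 0.40 − 0.45 = −5 points |
| 0.7 | 0.450 − 0.478 = −2.8 points | 0.36 − 0.43 = −7 points |

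Rejection rates were simulated with a stratified (Cochran-Mantel-Haenszel) test at the first Holm step, alpha 1.67%, with 200,000 replicates. For q = 0.3/0.5/0.7 they are about 2.4/1.6/2.4% for completers and 2.9/5.0/8.6% with lost as failures.

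If the rule adds only 5 points (15% versus 10%), the shifts are +1.3/0/−1.3 points for completers (error about 1.8/1.6/1.8%). With lost as failures they are −1.5/−2.5/−3.5 points (about 2.0/2.5/3.1%).

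**Power under the planned effect, equal 20% loss in both arms.**

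- Completers, taking loss as unrelated to outcome: 80 per arm, 50% versus 75%. Φ[(0.25·√80 − 2.394 × 0.6847)/0.6614] = Φ(0.90) = 81.7%.
- Lost as failures: 100 per arm, 0.8 × 50% = 40% versus 0.8 × 75% = 60%. Φ[(0.20·√100 − 2.394 × 0.7071)/0.6928] = Φ(0.44) = 67.1%.

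The missing-outcome rule alone therefore moves power by almost 15 points at the same loss.

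**The case against.** The strongest reply is that 7.3 is headed as a rule about treatment, two of its three bullets speak of treatment, and the "or" may mean whichever phase the patient is in. Entering follow-up and later leaving it are compatible, so a reader who infers a flat contradiction between 3.4 and 7.3 goes too far. That stands: the wording is unclear, and the sections need to be reconciled. But 7.3 names follow-up explicitly, and nothing elsewhere says that outcome visits continue after stopping.

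Second, missed appointments and a family's wish to leave would often cause loss under any wording. Only failure to follow instructions and poor hygiene clearly remove patients who would still attend, so the rule itself may add little loss. That also stands, and it is why the illustration gives both arms a 10% background loss.

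Third, intent-to-treat already keeps patients in their assigned arm, and the success definition already makes surgery a failure. True, but neither supplies a value for an unobserved outcome.

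A reader might also infer that root integrity is unmeasured in patients whose canine has erupted, because 5.1 specifies recall radiographs only for unerupted canines. The flowchart in 3.6 lists the long cone radiograph, if needed, at all three recalls without that limit, so the documents do not settle this. It is a question about endpoint measurement in patients who complete follow-up, and is not part of this point.

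**Conclusion.** The point holds as a cheap improvement that should be made. It is certain that the plan states no rule for a missing 18-month outcome and nothing that keeps outcome collection going after stopping. That 7.3 ends follow-up for patients who would still attend depends on reading it literally.

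The size is unknown. Under the assumed 20% versus 10% loss, the effect is modest for completers (at most 2.8 points) and larger if lost patients count as failures (3 to 7 points).

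A reader might infer severe inflation of error. Under the same assumptions, rates of about 17% or 36% do arise, but only with 20% loss in one arm, none in the other, and lost patients counted as failures (q = 0.5 or 0.7). The plan states neither such loss nor that rule. Nor can one say that power is safe because 100 per group exceeds 78: that margin covers about 22% equal loss in a completer analysis, but not if lost patients count as failures. Section 8.1 attributes the increase to the prediction model, and extra patients do not remove bias.

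**What to change.** Reconcile 3.4, 7.3 and 8.2.

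- In 7.3, leave the criteria for stopping treatment unchanged. Add that stopping, or not starting, the assigned treatment does not end outcome collection at the scheduled 6-, 12- and 18-month recalls unless consent to follow-up is withdrawn. Record the reason for each missed recall.
- In 8.2, state that every randomised patient is analysed in the assigned arm, and that components settled before loss are used: surgical exposure is a failure, and eruption seen at an earlier recall counts for the eruption component.
- In 8.2, name one primary method for outcomes still missing and say how it feeds the stratified test. Multiple imputation using arm, stratum and last recorded canine status is one option. Add a sensitivity analysis that varies success among the lost separately by arm.

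The cost is one or two sentences in 7.3, a paragraph in 8.2, and a little more analysis. Sites need some effort to recall stopped patients. Those patients would then have the examinations and radiographs that the protocol already schedules, and none beyond that schedule. Because section 17 has each site run the trial autonomously, all sites need the same instruction.

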- If the canine has erupted, a reevaluation of the specific presenting malocclusion will be performed and the need for further orthopedic or fixed appliance treatment will be discussed with the patient or his/her parents/guardians. Normal orthodontic treatment can be performed if desired. Only at the end of orthodontic treatment or, in case of no treatment need, at the end of late mixed dentition transition into permanent dentition, a last follow up visit will be planned in order to evaluate the end result.
- If the canine has not erupted yet, a long cone apical radiograph will be taken for evaluation of the canine position.
 - If a difference in vertical position is found when comparing with the LCAR taken during the last follow up visit, showing positive progression in canine eruption, reevaluation will take place after 6 months (= follow up visit 18 months).
 - If canine position between 6 and 12 months follow up remains unchanged, a CBCT might be indicated to evaluate canine position and its relation to the neighboring teeth. Depending on the CBCT evaluation, it might be decided to surgically expose the canine, either via a closed or open technique depending on its position. When the canine is exposed, further active orthodontic treatment will be needed to guide the canine into its position in the dental arch. Only at the end of orthodontic treatment, a last follow up visit will be planned in order to evaluate the end result, being the final position of the maxillary permanent canine in the dental arch.

Follow up 18 months

- If the canine has erupted, a reevaluation of the specific presenting malocclusion will be performed and, in case this should not have been made already, the need for further orthopedic or fixed appliance treatment will be discussed with the patient or his/her

parents/guardians. Normal orthodontic treatment can be performed if desired. Only at the end of orthodontic treatment or, in case of no treatment need, at the moment the canine reaches its final position in the dental arch, a last follow up visit will be planned in order to evaluate the end result.

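### The only blinding described covers a secondary measure (canine inclination on OPG); none is described for adjacent-root integrity or the LCAR judgement of progress, which feed the primary endpoint.

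*Combined protocol and SAP*

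**What the plan says.** Section 8 lists the measures against bias. The one blinding measure is that "measurements of canine inclination on OPG will be taken by two operators", who are blinded to each other's readings "as well as to the name of the patient, treatment followed or occlusion details". Section 6 places this quantity among the secondary efficacy parameters ("Improvement of canine angulation (root and crown tip"). It names eruption and root integrity of the adjacent teeth as the primary ones.

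Section 8.1 fixes the endpoint: "Success of the approach is defined as eruption without necessity of surgical intervention and integrity of the roots of the adjacent teeth". It adds: "The primary endpoint is defined as the percentage success after 18 months".

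Section 3.4 assigns two tasks to the LCAR: finding resorption of the lateral incisor and recording the vertical position of the canine. Section 5.1 then compares LCARs at 12 months for canines that have not erupted. Visible progress leads to another recall. Otherwise, "If canine position between 6 and 12 months follow up remains unchanged, a CBCT might be indicated", and after the CBCT "it might be decided to surgically expose the canine". No threshold for unchanged position is given, and no assessor is named.

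The flowchart in section 3.6 puts the panoramic film at screening and end result only, and the LCAR at screening and at 6, 12 and 18 months. The blinded OPG reading therefore does not use the films scheduled at the follow-up visits.

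**The concern.** The plan protects a secondary measurement and describes no protection for the parts of the primary endpoint that need radiographic judgement. The randomised options are expansion, extraction of the deciduous canines, and no treatment (section 3.4). Follow-up takes place at routine clinical visits where these can be seen.

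An assessor who expects an untreated canine to do badly may read a doubtful lateral incisor root as resorbed, or a doubtful LCAR pair as unchanged, more readily in the no-treatment arm. Either reading can turn a success into a failure in one arm only. The result is an apparent treatment difference where none exists. A larger sample, intention-to-treat analysis or the Bonferroni-Holm correction would not remove it.

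**Working it through.** **1. Which components are exposed to assessment bias**

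| Component of success | How it is judged | Masking described |
|---|---|---|
| Eruption | Clinical: the canine perforates the mucosa into the arch (section 5.1, End result) | None, but fairly objective |
| No need for surgery | LCAR at 6 v 12 months, then CBCT, then a discretionary decision (section 5.1) | None |
| Integrity of adjacent roots | LCAR (section 3.4); CBCT if there is evidence of damage; end-result films | None |
| Canine inclination (not part of success) | OPG, two operators | Yes |

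**2. When a biased surgery decision changes the result**

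Success requires eruption, so a canine unerupted at 18 months fails whether or not it was exposed. The decision matters only if all four of these hold:

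- the canine is unerupted at 12 months;
- it is called unchanged since 6 months;
- it is exposed after CBCT;
- it would otherwise have erupted by 18 months.

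Root scoring is the second route. It can affect any patient whose canine erupts.

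**3. The plan's own figure**

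Inputs from section 8.1: 50% v 75%, power 80%, two-sided alpha 0.05/3 = 0.0167 (z = 2.394; z for power = 0.842). The mean proportion is 0.625.

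n = [2.394 × √(2 × 0.625 × 0.375) + 0.842 × √(0.5 × 0.5 + 0.75 × 0.25)]² / 0.25²

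= [2.394 × 0.6847 + 0.842 × 0.6614]² / 0.0625 = 77.1, rounded up to 78.

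This agrees with the plan. At 100 per group the power is 90.3%.

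**4. Illustration of what a shift would do**

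Assumptions, none of them given in the documents: true success is p = 60% in both arms, and biased assessment lowers recorded success by d in one arm. The calculation uses n = 100 per arm and one unstratified pairwise test at 0.0167.

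Rejection probability = Φ[(d − 2.394 × s0)/s1] + Φ[(−d − 2.394 × s0)/s1], where s0 and s1 are the pooled and unpooled standard errors.

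For d = 0.05 (0.60 v 0.55), s0 = √(2 × 0.575 × 0.425/100) = 0.0699 and s1 = √((0.24 + 0.2475)/100) = 0.0698. This gives Φ(−1.681) + Φ(−3.113) = 0.0464 + 0.0009 = 4.7%.

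| Shift in one arm | Normal approximation | Exact binomial |
|---|---|---|
| 0 points | 1.7% | 1.7% |
| 1 point | 1.8% | 1.9% |
| 2 points | 2.1% | 2.2% |
| 3 points | 2.7% | 2.9% |
| 5 points | 4.7% | 5.1% |
| 10 points | 16.4% | 17.7% |

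Across true success of 50% to 75%, the normal approximation gives 4.7 to 5.5% for 5 points and 16 to 20% for 10 points.

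**The case against.** **The protocol never says that the assessors know the arm.** A reader might infer that the endpoint is scored by unblinded clinicians. The documents do not say who scores it or what they know. What stands is that no masking is described, in a trial whose treatments show in the mouth.

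**The surgery route is narrow and the shifts are invented.** Both points are fair. Only the subset in step 2 of the working is affected, and the documents do not give its size. At 60% success, a 10-point shift means losing 10 of 60 successes in an arm, and shifts of 1 to 3 points do little. The test shown is also not the planned stratified test with Holm correction. The table shows sensitivity and is not a forecast.

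**The films do not cover everyone.** Section 5.1 specifies follow-up LCARs only for unerupted canines. At 18 months the LCAR may also be omitted when clinical signs are clear. The candidates for success may therefore have only an end-result film, possibly after orthodontic treatment averaging 24 months (section 4.3). This limits what masked reading can deliver, but the films that exist can still be read masked.

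**Masking is imperfect and sites are separate.** An absent deciduous canine can reveal extraction, which enters two of the three comparisons. Sites also run autonomously without third-party funding (section 17). These costs are real, but they do not outweigh partial protection of the primary endpoint.

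**Conclusion.** The gap is real and should be closed. As written, the plan leaves root-integrity scoring and the LCAR judgement of progress open to assessment bias, while its masked readers work on a secondary measure.

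The size cannot be derived from the documents. Under the stated assumptions, a 5-point shift roughly triples the nominal 1.67% error of one pairwise test, and a shift of 1 to 3 points barely moves it. The conclusion rests on one inference, that assessors are likely to know the arm.

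Two stronger readings should be resisted. The first is that every surgery decision contaminates the endpoint; the eruption requirement rules that out. The second is that need for surgery should be redefined from masked film progress. For a canine already exposed, unassisted eruption is unknown. A canine that is static at 12 months and then erupts unaided with intact roots would be called a failure, against section 8.1.

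**What to change.** Add the following to section 8:

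- The same two operators, masked to name and treatment, read whichever existing films are used to score root integrity: baseline, and any follow-up LCAR, CBCT or end-result film. They use criteria written in advance. Their reading supplies the root component of the primary endpoint.
- They also score progress or no progress on the paired 6- and 12-month LCARs. Agreement with the treating clinician's judgement, and with exposure, is reported by arm as a supportive check on differential referral. The primary endpoint is not redefined from this score.
- State the limits: masking is incomplete where a missing deciduous canine reveals extraction, and for canines that erupt early, root status may rest on the end-result film, possibly after orthodontic treatment.

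No new films or visits are needed, and the decision to operate stays with the treating clinician. The cost is reading time, plus de-identification and transfer of films across sites.
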